Impact of TOtally transdErmal Sedation in the weaning from remifentanil infusion among critically ill patients undergoing mechanical ventilation: a pilot randomized-controlled Study (The TOES Trial)

NCT04204967

24/02/2020 versione n°3

Abstract

Rationale and Background: The choice of the sedation protocol has a massive impact on the duration of mechanical ventilation and the timing of extubation. Many sedation protocols are described in the literature. No data are available about the possibility of using TTS-fentanyl as an alternative to intravenous opioids during the weaning phase from mechanical ventilation and the post-extubation period until the discharge from ICU to the ward. **Objective:** We aim to assess if a TTS fentanyl-based sedation protocol can have an impact on the global Work of Breathing (WOB). Secondary endpoints of the study are the duration of mechanical ventilation, the duration of continuous infusion of opioids, the length of stay in ICU and in hospital. **Methods:** We will perform a 2-arm, single-center, prospective randomized controlled trial. The duration of the study will be approximately one year, for a total of 24 patients. Patients ventilated in pressure support ventilation (PSV) receiving continuous intravenous remifentanil for more than 5 days will be considered eligible. Eligible patients will be randomized in 2 groups: Group 1 will receive remifentanil; Group 2 will receive TTS-fentanyl and remifentanil. Patients will be selected from the population admitted to the adult ICU (a 20-beds unit), the post-operative ICU (a 13-beds unit), and the NeuroICU (a 10-beds unit). An Edi Catheter for diaphragm electrical activity monitoring will be put in place for each patient. **Outcomes:** The primary endpoint is to demonstrate that the area under the curve (AUC) of the work of breathing per minute in the intervention group is not higher than the control group. Secondary endpoints are differences respiratory rate, tidal volume, arterial blood pressure, heart rate, global duration of mechanical ventilation and opioids infusion, length of stay in ICU and in hospital. **Statistical Analysis:** Distribution normality will be assessed with the Kolmogorov-Smirnov test. Continuous variables will be reported expressed as medians (interquartile ranges). Qualitative variables will be reported as frequencies. Analysis on the primary efficacy criterion and other quantitative variables will be assessed with the Wilcoxon-Mann-Whitney test. Categorical outcomes will be compared with the chi-square test, or Fisher's exact test, as appropriate. Cochran-Mantel-Haenszel statistics will be reported for all these results. Two-way analysis of variance (ANOVA) for repeated measures with Bonferroni correction will be used to determine the differences in secondary endpoints. Comparisons between groups regarding these variables at each study time point were performed with the Student's t-test or Mann-Whitney test, as appropriate. Mean difference and 95% confidence interval [CI95%] are reported for most significant results. Two-tail p values≤0.05 Will be considered significant.

Exclusion criteria	
 • Hypoxemic respiratory failure ($P/F < 200$ mmHg); • Haemodynamic instability requiring high doses of inotropes or vasopressors; • Current enrollment or plan to enroll in any interventional clinical study in which an investigational treatment or approved therapy for investigational use is administered within 30 days or 5 half-lives of the agent, prior to the baseline visit; • Any condition that may contraindicate the use of remifentanil or transdermal fentanyl; • Patient admitted for post-operative monitoring after elective surgery; • EAdi catheter contraindicated. • Hypersensitivity to the active substance or any of the excipients; • Hepatic or renal impairment; • Fever (body temperature ≥ 38 °C) or septic shock, hypothermia (body temperature < 35 °C) or presence of active surface cooling systems; • Hypercapnic patients with a $PaCO_2 > 45$ mmHg; • Delirium state defined as RASS ≥ 3 and CAM-ICU positive; • Patients with a BMI ≥ 35.
Primary Objective	To assess if a transdermal fentanyl-based sedation protocol is at least non-inferior when compared to a totally intravenous remifentanil infusion protocol. we will compare the global work of breathing (WOB) of the patients randomized to receive transdermal fentanyl vs. remifentanil alone. We will calculate the area under the curve (AUC) of the work of breathing per minute in the intervention group vs the control group
Secondary Objectives	Main secondary endpoints include differences in respiratory rate, tidal volume, arterial blood pressure, heart rate, global duration of mechanical ventilation, length of stay in ICU and in hospital.
Number of Patients	N = 24

Statistical Analysis	
Distribution normality will be assessed with the Kolmogorov-Smirnov test. Continuous variables will be reported expressed as medians (interquartile ranges). Qualitative variables will be reported as frequencies. Analysis on the primary efficacy criterion (AUC of the work of breathing) and other quantitative variables will be assessed with the Wilcoxon-Mann-Whitney sum of rank test. Categorical outcomes will be compared with the chisquare test, or Fisher's exact test, as appropriate: Cochran-Mantel-Haenszel statistics will be reported for all these results. Two-way analysis of variance (ANOVA) for repeated measures with Bonferroni correction will be used to determine the differences in work of breathing per breath, inspiratory effort, delta EAdi, plateau pressure, P 0.1 respiratory rate, tidal volume, arterial blood pressure, heart rate in the two groups. Comparisons between groups regarding these variables at each study timepoint were performed with the Student's t test or Mann-Whitney test, as appropriate. Mean difference and 95% confidence interval [CI95%] are reported for most significant results. Two-tail p values≤0.05 Will be considered significant. Statistical analysis will be performed with SPSS software package (SPSS Inc. Released 2009. PASW Statistics for Windows, Version 18.0. Chicago: SPSS Inc.).

-----------------------------	---

1. Rationale and Background

Invasive mechanical ventilation is a lifesaving intervention among critically ill patients. However, prolonged ventilation is associated with increased morbidity and mortality. Optimal processes for weaning from ventilation have been studied for many years and have led to evidence-based clinical practice guidelines to facilitate early liberation from invasive mechanical ventilation. It is crucial to avoid prolonged MV, and weaning from the mechanical ventilator should not be delayed to avoid complications as VAP, weakness and atrophy of respiratory muscles, and the need for a tracheostomy (Jeong et al. 2015; Béduneau et al. 2017; Girard et al. 2017; Peñuelas et al. 2011; Perkins et al. 2018).

The choice of the sedation protocol has certainly a massive impact on the duration of MV and the timing of extubation. Many different sedation protocols are described in the literature and adopted in every day clinical practice. A hypnotic agent, propofol or midazolam, is commonly used in combination with an opioid in infusion, typically remifentanil, fentanyl or sufentanil. However, analgesia-based sedation techniques, which focus on patient comfort rather than on patient sedation by catering to the analgesic needs of the patient and adding a sedative only if necessary, are well established in the ICU setting.

1.1 Remifentanil

Remifentanil is a selective μ opioid receptor agonist indicated for use during anesthesia and for the provision of analgesia in mechanically ventilated critically patients. Remifentanil has an onset of 1 min and quickly achieves a steady state. Differently, from other opioids, it is metabolized by non-specific blood and tissue esterases into a clinically inactive metabolite, resulting in an elimination half-life of fewer than 10 minutes and not correlated at all with the infusion duration. The unique pharmacological profile of remifentanil has proved particularly advantageous in ICU patients (Muellejans et al. 2004). Muellejans et al. randomly compared remifentanil versus propofol-fentanyl sedation regimen in ICU, showing that remifentanil alone allowed the adequate provision of optimal sedation and rapid extubation without the need for propofol in the majority of patients. Remifentanil was associated with less between-patient variability in the mean percentage of time with optimal sedation than was fentanyl. Using conventional opioids such as fentanyl, however, would require constant patient monitoring to avoid over-sedation caused by drug accumulation, resulting in delayed extubation (Muellejans et al. 2004). An RCT published by Akinci et al. comparing remifentanil to fentanyl infusion in postoperative children confirmed the advantages given by the use of remifentanil, but the authors suggested that the short elimination time of remifentanil may also cause some disadvantages. The elevated heart rates, blood pressures, and the increased sedation scores after cessation of remifentanil probably reflected the short elimination time of remifentanil. Moreover, a higher incidence of pain was noticed after end of the remifentanil infusion and probably this could benefit from long-acting analgesic administration before the cessation (Akinci et al. 2005). 23 RCTs with a total of 1905 patients were included in a recent systematic review and meta-analysis comparing remifentanil infusion with other opioids in mechanically ventilated patients. The results of this meta-analysis suggested that the use of remifentanil was associated with a reduction in the duration of mechanical ventilation when compared with other opioids, specifically with fentanyl infusion, probably related to the pharmacokinetics and pharmacodynamics of remifentanil, its rapid onset and offset. Remifentanil

was associated with reductions in time to extubation after sedation cessation and ICU length of stay but not reductions in hospital length of stay or costs.

Moreover, neurologic assessment is essential for neurosurgical and neurotrauma patients, and the association between remifentanil and rapid and predictable awakening may be more meaningful in these patients(Zhu et al. 2017). Futier et al. in a retrospective study comparing remifentanil to sufentanil suggested that using a short-acting opiate with short context-sensitive half-life in an analgesia-based sedation protocol may significantly decrease the duration of mechanical ventilation and the ICU length of stay even though not significantly in long term sedation, while improving the achievement of sedation goals despite a lower requirement for adjunctive hypnotic agents (Futier et al. 2012). Moreover, remifentanil is demonstrated to reduce inspiratory muscle effort and improve ventilatory patterns in mechanically ventilated patients with tachypnoea or rapid shallow breathing resulting in an effective choice for patients who remain tachypnoeic during weaning from mechanical ventilation(Natalini et al. 2011).

1.2 TTS-fentanyl

Fentanyl was the first in a class of potent synthetic opioid analgesics developed in the 1960s. Restricted to anesthesia until the 1990s when the development of non-injectable fentanyl formulations was intensively pursued. Nowadays, transdermal fentanyl patches are among the most frequently prescribed strong opioid analgesics. As for remifentanil, fentanyl is another pure μ opioid receptor agonist. Fentanyl is extensively metabolized, and renal excretion accounts for only 10 % of the dose. Passive Transdermal Therapeutic Systems (TTS) use the matrix technique with the drug dissolved in an inert polymer matrix that controls drug release. Delivery results from the concentration gradient between fentanyl in the patch and the skin. Transdermal fentanyl patches constantly deliver 12.5, 25, 50, 75 or 100 mcg/h over 72 h. The amount delivered is proportional to the surface of the resorption area, fentanyl can be detected in plasma after 1–2 h, but the onset of the full analgesic effect is obtained between 12 and 24 h after patch application and may vary with local conditions such as skin temperature. For example, during fever, fentanyl plasma concentrations can increase by approximately 33 % at body temperatures of 40 C. Transdermally delivered fentanyl is not subject to first-pass metabolism and providing a great bioavailability, near 92%(Newshan 1998; Carter 2003; Lötsch et al. 2013). High doses of TTS-fentanyl is documented to have an effect on the respiratory drive, causing respiratory depression, as a potential danger of any technique maintaining constant blood opioid concentrations, as described in an old study performed on post-operative patients comparing high doses of TTS-fentanyl vs. placebo(Bülow et al. 1995).

1.3 IMP-dose rationale

Different patches delivering different doses of fentanyl are available (12.5 mcg/hr, 25 mcg/hr, 50 mcg/hr, 75 mcg/hr, 100 mcg/hr). Because we had to choose only one, we decided *a priori* to adopt a TTS-fentanyl patch delivering 25/hr of the active principle. The reason for this choice was that it is more practical for us to titrate the dose. The starting dose will be 50 mcg/hr (two patches) and, based on the PaCO₂ values, can be increased or decreased every 24 hours, adding or removing two (50 mcg/hr) or three patches (75 mcg/hr). According to the study protocol, the maximum achievable dose of fentanyl is 300 mcg/hr. Due to the completely new usage that we are proposing for this drug, there is a lack of information in the literature about which is the maximum dose administrable to patients. In the *Summary of Product Characteristics* of TTS-fentanyl is specified

that: *“Some patients may require additional or alternative methods of opioid administration when the TTS-fentanyl dose exceeds 300 mcg/hr”*. The conclusion is that we decided not to exceed 300 mcg/hr of transdermal fentanyl.

Moreover, more considerations need to be done:

- We use TTS-fentanyl to wean the patient from remifentanil, a much more stronger opioid routinely used in Intensive Care Unit (ICU);
- Patients in ICU are strictly monitored 24 hours a day and mechanically ventilated, so the risks for respiratory depression is minimum;
- Remifentanil is traditionally infused at rates that may vary from 0.0125 to 0.25 mcg/kg/min. Using tables available for opioid conversion, we can estimate that 300 mcg/hr of transdermal fentanyl corresponds to 180 mg/day of intravenous (IV) morphine and so 1,80 mg of remifentanil. In a subject of 70 kg, 1,80 mg/day of remifentanil correspond to 0,0178 mcg/kg/min of infusion rate, a very low dose for ICU standards (see APPENDIX 3).

1.4 EAdi and monitoring of the electrical activity of the diaphragm

Diaphragm dysfunction frequently develops in mechanically ventilated ICU patients and is associated with adverse clinical outcomes, including prolonged mechanical ventilation and mortality. Diaphragm electromyography (EMG) is a technique used to quantify breathing effort in ICU patients. A correlation has been reported between the electrical activity of the diaphragm (EAdi) and trans-diaphragmatic pressure (P_{di}) or esophageal pressure (P_{es}). The $P_{musc}/EAdi$ index (PEI), also known as neuromechanical efficiency, defined as the ratio of the change in airway pressure (ΔP_{aw}) to $\Delta EAdi$ during an end-expiratory occlusion ($PEI_{occl,paw}$), has been used to estimate the inspiratory effort breath by breath. This ratio describes how much pressure can be generated for each microvolt of EAdi signal, in other words, how efficient the diaphragm is in generating pressure for a certain amount of electrical activity (BECK et al. 2001; Bellani et al. 2013; Liu et al. 2010; Jansen et al. 2018). The proportionality between EAdi and the pressure developed by respiratory muscles (P_{musc}) is well described:

$$P_{musc}_{EAdi} = EAdi \cdot PEI_{occl,paw}$$

Bellani and coworkers demonstrated that $PEI_{occl,paw}$ is a good surrogate of the PEI measured during regular tidal ventilation (PEI_{dyn}), thus allowing a clinically valuable estimate of inspiratory effort without the need for P_{es} monitoring. Moreover, Bellani showed that $PEI_{occl,paw}$ is a good estimate of PEI_{dyn} but slightly overestimated probably because of the more favorable condition of the diaphragm in the absence of flow. They deduced that $PEI_{occl,paw}$ needs to be corrected by a factor of 1.25(Bellani et al. 2013). It is, therefore, possible to obtain a continuous calculation of P_{musc} based on EAdi and $PEI_{occl,paw}$ without knowing the P_{es} value. From P_{musc}_{EAdi} two commonly accepted indexes of inspiratory effort can be obtained: the maximal P_{musc} of the respiratory cycle and the pressure-time product (PTP_{EAdi} , the integral of P_{musc}_{EAdi} during inspiration).

No data are available in the literature about the possibility of using TTS-fentanyl as an alternative

to intravenous opioids during the weaning phase from mechanical ventilation and the post-extubation period until the discharge from ICU to the ward. There is only a case-report documenting the use with success of TTS-fentanyl for a patient who developed central hyperventilation(Adachi et al. 2007).

Our hypothesis is that, due to the intrinsic pharmacokinetics and pharmacodynamic characteristics of TTS formulation of fentanyl, it can have a role in weaning the patient from intravenous opioids, such as remifentanil, and mechanical ventilation, reducing the duration of MV itself. It can have also an impact on costs allowing the discharge to the ward of patients with an ongoing patch.

2. Study Objectives and Endpoints

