2.2 Primary Endpoint

To demonstrate that the area under the curve (AUC) of the work of breathing per minute (assessed at 1, 6, 12, 24 hours for the first day after randomization, and every 24 hours for the following days) in the intervention group is not higher than the control group. We will also analyze differences in work of breathing per breath, inspiratory effort, delta EAdi, plateau pressure, driving pressure, transpulmonary driving pressure, pulmonary compliance, P0.1, P/F ratio.

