- If in the meantime, the patient is weaned from the mechanical ventilator, extubated, spontaneously breathing, and unable to cooperate we will use as a surrogate the neuromechanical efficiency calculated when the patient was connected to the ventilator. The recording will last only 10 minutes.

We will calculate $PEI_{occl,paw}$, the $Pmus_{EAdi}$ waveform, and the two most validated indexes of inspiratory effort: $\Delta Pmus$ and the PTP_{EAdi} (a good indicator of the metabolic work of breathing). We will analyze the dynamic transpulmonary driving pressure, corresponding to the sum of the pressure support level and $Pmus_{dyn}$, and representing a surrogate of dynamic stress that takes into account the chest wall elastance. Moreover we will measure the plateau pressure, the positive end-expiratory pressure (PEEP), and we will calculate the driving pressure and the static compliance of the respiratory system.

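### Section 1.4 defines the efficiency index on the change in EAdi but multiplies it by EAdi itself, so any resting EAdi enters maximal Pmusc and PTP_EAdi as a patient-varying additive error

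*Combined protocol and SAP*

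**What the plan says.** Section 1.4 introduces the index as a ratio, "defined as the ratio of the change in airway pressure" "to $\Delta EAdi$ during an end-expiratory occlusion", so PEI_occl,paw is a slope between two changes. It then gives the muscle-pressure waveform as "P_{musc}_{EAdi} = EAdi \cdot PEI_{occl,paw", where EAdi carries no delta and no baseline is subtracted. Two indexes are taken from that waveform: "the maximal P_{musc} of the respiratory cycle" and the pressure-time product PTP_EAdi, which is "the integral of P_{musc}_{EAdi} during inspiration". The section also mentions a multiplicative correction of 1.25 for the index.

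Section 4.3.1 says the trial will calculate PEI_occl,paw, the Pmus_EAdi waveform "and the two most validated indexes of inspiratory effort", here named as delta-Pmus and PTP_EAdi. It describes PTP_EAdi as indicating the metabolic work of breathing. It gives no other formula for the waveform.

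Section 2.2 sets the primary endpoint as the AUC of work of breathing per minute and lists "inspiratory effort, delta EAdi, plateau pressure" among further variables. Section 6 plans a Wilcoxon-Mann-Whitney test for the primary variable. No section says how end-expiratory EAdi is handled, and none gives an equation for work of breathing per minute.

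**The concern.** A slope estimated from changes should be multiplied by a change. Multiplied by the raw signal, it gives a positive muscle pressure at end-expiration, when there is no inspiratory effort, whenever EAdi does not return to zero between breaths. The surplus is PEI times the resting EAdi. It varies with the patient's resting activity and efficiency and, once integrated and summed per minute, with inspiratory time and respiratory rate. The factor of 1.25 rescales the surplus but cannot remove it.

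The peak index also differs between sections. Maximal Pmusc (1.4) contains the surplus and delta-Pmus (4.3.1) does not. Two analysts following the text could obtain different effort values from the same recording. PTP_EAdi is the measure the plan ties most closely to work of breathing, so a contaminated PTP could blur the comparison on which a 24-patient trial depends.

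**Working it through.** **Inputs.** From the documents: the definition of PEI and the waveform formula (1.4), the indexes (1.4 and 4.3.1), the rank test (6) and 12 patients per arm (6.1; 10/0.9 = 11.1, rounded up to 12). The plan states no EAdi, PEI or timing figure, so there is none to reproduce. Every such value below is an assumption.

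**1. Algebra.** Write EAdi(t) = e0 + phasic(t), where e0 is the end-expiratory level, D the phasic swing, Ti the inspiratory time, RR the respiratory rate, and m the mean of the phasic part over inspiration as a fraction of D (0.50 for a ramp, 0.64 for a half-sine). The formula as written gives:

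- maximal Pmusc = PEI × (D + e0), which contains the offset;
- delta-Pmus = PEI × D, where the offset cancels;
- PTP per minute = PEI × RR × Ti × (m × D + e0), which contains the offset.

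Relative inflation of PTP = e0 / (m × D).

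**2. Inflation of PTP for e0 of 0.5 to 2 microvolts.**

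| Swing D (microvolts) | Smallest | Largest |
|---|---|---|
| 5 | 0.5/(0.64 × 5) = 16% | 2/(0.50 × 5) = 80% |
| 10 | 0.5/(0.64 × 10) = 8% | 2/(0.50 × 10) = 40% |
| 15 | 0.5/(0.64 × 15) = 5% | 2/(0.50 × 15) = 27% |

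**3. A common offset.** Assume half-sine swings of 12 and 9 microvolts, PEI 1, Ti 1 s, RR 25.

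- e0 = 0: PTP per minute is 25 × 12 × 2/π = 191.0 and 25 × 9 × 2/π = 143.2; difference 47.7, ratio 0.750.
- e0 = 2: each value rises by 25 × 2 = 50, to 241.0 and 193.2; difference still 47.7, ratio 0.802.

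Only the relative difference shrinks. Adding the same constant to every patient's value leaves ranks, and so the rank-test p value, unchanged.

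If RR is 20 in the lower-effort arm, the difference is 76.4 at e0 = 0. At e0 = 2 it is 76.4 + 2 × (25 − 20) = 86.4. The absolute difference widens, while the ratio moves from 0.600 to 0.641.

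**4. An offset that varies by patient, with the same distribution in both arms.** Assume e0 uniform on 0-2; swing lognormal with CV 50%; PEI lognormal with median 1.5 and CV 40%; RR 25 (SD 6); Ti 0.9 (SD 0.2); m = 0.6.

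- Median swing 10: mean swing = 10 × √1.25 = 11.18, and m × D = 6.71. Mean e0 is 1, so a true 20% fall shows as 0.20 × 6.71/(6.71 + 1) = 17.4%.
- Median swing 5: mean swing 5.59, m × D = 3.35, so it shows as 0.20 × 3.35/(3.35 + 1) = 15.4%.
- The mean of e0 is the same in both arms, so it drops out of the absolute mean difference. With mean PEI 1.5 × √1.16 = 1.616, that difference is 1.616 × 25 × 0.9 × 0.20 × 6.71 = 48.8 at swing 10, with or without the offset.
- Simulated rank correlation between PTP with and without the offset: 0.99 (swing 10) and 0.96 (swing 5).

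Simulated power of the two-sided Mann-Whitney test on PTP, 12 per arm, true fall of 40%:

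| Median swing | Baseline removed | Formula as written |
|---|---|---|
| 10 | 0.37 | 0.30 |
| 5 | 0.36 | 0.23 |

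For a 20% fall at swing 10, power is about 0.10 and 0.09, so little is left to lose.

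**5. Resting activity that differs by arm.** In a second simulation, the mean swing is 10, the fall is 40%, and RR and Ti are fixed. With equal resting EAdi of 0, 1 and 2 microvolts, power is 0.46, 0.39 and 0.31, and the mean difference stays at 63-64. If resting EAdi averages 2 microvolts but is lower in the lower-effort arm by a factor of 0.6 or 0.3, the mean difference rises to 83.8 or 98.9 and power to 0.57 or 0.76. The direction of the error therefore turns on facts that the documents do not give.

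**The case against.** The equation stands in the background section and is offered as a proportionality from earlier literature. The methods text names delta-Pmus, which is immune to a constant offset, and section 2.2 lists delta EAdi separately. The trial's software may already subtract a baseline. All of that is fair, but it does not dispose of the point. Section 4.3.1 promises the waveform and PTP_EAdi without another formula, so the one in 1.4 is all an analyst has, and PTP_EAdi does carry the offset.

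A reader might infer more: that differences between the arms shrink in general, and that this helps the claim that work of breathing is not higher. The documents do not support that. Steps 3 to 5 show absolute mean differences unchanged under equal resting activity, ranks unchanged under a common offset, and differences that widen under other patterns. Only the ratio shrinks reliably when resting activity is equal, and the plan specifies no ratio estimand. Any advantage that dilution gives to a not-higher claim comes from the absence of a stated margin, which baseline subtraction would not repair.

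Nor can harm to the primary endpoint be shown, because nothing in the plan leads from Pmusc or PTP to work of breathing per minute. It is also fair to say that rank correlations of 0.96 to 0.99 imply a modest effect, and that the 80% inflation pairs the largest assumed offset with the smallest assumed swing.

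**Conclusion.** The point holds as an internal inconsistency in a stated formula: the index is defined on a change and applied to a level. Followed literally, the text puts PEI times resting EAdi into maximal Pmusc and PTP_EAdi, but not into delta-Pmus. With resting EAdi of 0-2 microvolts and equal distributions in the arms, the cost is a dilution of a 20% relative fall to about 15-17%. For a 40% fall, the loss of power is about 0.07 at larger swings (0.37 − 0.30) and 0.13 at smaller ones (0.36 − 0.23). These sizes concern PTP and rest wholly on assumed EAdi, PEI and timing values. If resting EAdi is near zero there is no effect, and if it differs by arm the sign is open. For the primary variable the consequence is an inference only. The formula should be corrected before analysis because the change is nearly free and removes a choice otherwise left to the analyst. It does not by itself put the trial's conclusion in doubt.

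**What to change.** In sections 1.4 and 4.3.1, write Pmus_EAdi(t) = [EAdi(t) − end-expiratory EAdi of the same breath] × PEI_occl,paw. Use the same baseline when delta EAdi is read during the occlusion. Derive PTP_EAdi, and any work of breathing computed from this waveform, from the corrected version. Use delta-Pmus as the peak index in both sections in place of the maximal Pmusc in 1.4.

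The cost is one corrected formula and one line in the waveform processing. No new data are needed, since EAdi is already recorded as a waveform, and the sample size is unaffected. The downside is slight added noise from locating end-expiration in each breath.
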